## 16.6 Urgent Safety Measures

The CI will take urgent safety measures if necessary to ensure the safety and protection of the clinical study participant from immediate hazards to their health and safety. The measures will be taken immediately. The approval of the REC prior to implementing urgent safety measures is not required. However, the CI will inform the sponsor and Research Ethics Committee (via telephone) of this event immediately.

The CI will inform the REC in writing within 3 days, in the form of a substantial amendment. The sponsor (Joint Research Management Office (JRMO)) will be sent a copy of the correspondence with regards to this matter.

## 16.7 Annual Safety Reporting

The CI will send the Annual Progress Report to the REC using the HRA template (the anniversary date is the date on the REC "favourable opinion" letter) and to the sponsor.

## 16.8 Overview of the Safety Reporting responsibilities

The CI is the medical assessor on behalf on the sponsor and will review all events reported. The CI will ensure that safety monitoring and reporting is conducted in accordance with the sponsor's requirements.

The CVCTU will have oversight of safety reporting, and will monitor the study to ensure all SAEs are identified and reported in the required timelines to the Sponsor and REC as required.

## 17. Monitoring and auditing

The sponsor or delegate retains the right to audit any study, study site, or central facility. Any part of the study may be audited by the funders, where applicable.

The CVCTU will monitor the study, with reference to both the CVCTU's Standard Operating Procedure and following the study specific monitoring plan. Monitoring will be conducted to ensure data integrity and patient safety, as well as compliance to the protocol and GCP. Both on-site visits and central monitoring of data via the REDCap database will be performed. Monitoring reports will be written and made available to the Sponsor. Monitoring will include source data verification, query resolution and review of GCP and protocol compliance. Protocol deviations will be logged in the Trial Master File and be reported to the Chief Investigator and Sponsor. Frequently recurring breaches are not acceptable and will require immediate action to prevent the variations.

The Joint Research Management Office (JRMO) of Barts Health NHS Trust may audit the study to determine whether the trial related activities were conducted, and that data were recorded, analysed and accurately reported according to the protocol, CVCTU's Standard Operating Procedures and Good Clinical Practice (GCP). Audits will be triggered:

- if the JMRO's identifies a need during the risk assessment process.
- following an allegation of research misconduct or fraud or a suspected breach of regulations
- at random

## 18. Trial committee and investigator arrangements

### 18.1 Trial steering committee (TSC)

A Trial Steering Committee will be constituted and will be chaired by an independent expert. It will be set up and run according to the principles outlined in the CVCTUs Standard Operating Procedure. Terms of reference (TOR) for committees will be agreed before the commencement of the trial. All members of committees must agree and sign the TOR before recruitment into the trial begins. Meetings will be formally minuted with actions recorded and stored in the Trial Master File.

The TSC will provide oversight to the conduct of the study on behalf of the study Sponsor and Funder.

The TSC will meet at least after the first two patients are recruited or at least every 6 months either face to face or by teleconference. Meetings will be scheduled in parallel with the DSMC meetings, typically following the DSMC. Observers from the Sponsor and Funder will be invited and may be in attendance.

### 18.2 Data Safety and Monitoring Committee (DSMC)

A Data Monitoring and Safety Committee will be constituted that will be chaired by an independent expert. It will be set up and run according to the principles outlined in the CVCTU's Standard Operating Procedure. Terms of reference (TOR) for committees will be agreed before the commencement of the trial. All members of committees must agree and sign the TOR before recruitment into the trial begins.

The DSMC will be responsible for:

- monitoring any trial data
- making recommendations to the TSC on whether there are any ethical or safety reasons why the study should not continue
- advising the TSC regarding the release of data and/or information
- consider data emerging from other studies.

The DSMC will meet after the first two patients are recruited or at least every 6 months either face to face or by teleconference. Additional meetings may be convened at the request of the DSMC

or if there are any safety concerns. Observers from the Sponsor and Funders will be invited and may be in attendance.

### **18.3 Investigators**

The investigators are responsible for ensuring that the study is conducted according to this protocol and any applicable regulations.

All investigators will have undergone a training program that aims to provide each investigator with a thorough working knowledge of the protocol, study manual, associated standard operating procedures and applicable regulations and competence to perform their specific roles. The specific requirements are outlined in the latest version of the Study Training Manual.

All investigators will have undergone Good Clinical Practice training in the previous two years and will renew this appropriately.

The Chief Investigator will ensure that the study records are complete, accurate and current. These records will include the following materials:

- Correspondence with the Sponsor, the Trial Steering Committee, the investigators, the funders and the Research Ethics Committee (REC).
- Accountability of records of receipt, use, and disposition of all investigational devices and study materials, including the type and quantity, date of receipt, any serial/batch number and the names of all persons receiving, using and disposing of such items
- Study Subject Records, including Informed Consent forms, copies of all completed Subject Case Report Forms (CRFs) and supporting documents (laboratory reports and reports of diagnostic tests, medical records, etc.).
- All relevant observations, including records concerning adverse events (whether anticipated or unanticipated)
- Current study protocol and protocol deviation log, with dates and details of any reason for deviations from the protocol that could affect the scientific quality of the study or the rights, safety, or welfare of the subjects
- The approved blank Informed Consent form and blank Subject CRFs
- Certification that the Protocol has been approved by all of the necessary approving authorities
- Signed Investigator's Agreements with curricula vitae of all participating Investigators

The Chief Investigator will be responsible for the following reports:

- Serious adverse events
- Deviations from the investigational plan
- Annual progress reports to the study Sponsor, Funders and REC.
- Final report to the study Sponsor, Funders and REC. The end of study declaration will be made to the REC within 90 days of the end of the study, and the end of study report will be submitted within 1 year of the end of study. This will be produced irrespective of whether the study finishes as scheduled or is terminated early.

## **19. Finance and funding**

This study is funded by:

- London's Air Ambulance Charity through an unrestricted research grant
- Barts Charity through an unrestricted research grant
- Maquet Cardiopulmonary GmbH through unrestricted funding that provides free ECMO disposables to the study.

## 20. Indemnity

The NHS indemnity scheme will apply. It provides cover for the design, management, and conduct of the study.

## 21. Dissemination of research findings

A manuscript summarising the study will be drafted by the chief investigator following completion of the study. It will be formulated according to the Consolidated Standards of Reporting Trials (CONSORT) guidelines and the Template for Intervention Description and Replication (TIDieR) checklist and guide [26, 27] The chief investigator will be responsible for the integrity of the data contained within the manuscript and accuracy of the analysis. All investigators will have full access to the data and provide interpretation and critical revision of the manuscript. Any funders will have no role in the preparation, review or approval of the manuscript.

Authorship credit will be according to internationally agreed guidelines ([www.icmje.org](http://www.icmje.org)) that require authors to fulfil all of the following criteria:

- substantial contributions to the conception and design, or acquisition of data, or analysis and interpretation of data
- drafting the article or revising it critically for important intellectual content

An electronic version of published research papers will be made freely available in Europe PubMed Central as soon as possible and definitely within 6 months of publication. We will share an electronic version of the manuscript with patients who participated in the study and any patients and publics involved in the study design and conduct.

Any results communicated via the press, social media or internet will be done following consultation and agreement of the press officers of Barts Health NHS Trust and the funders.

All research participants will be informed of the results via letter with 6 months of the study ending.

AE	Adverse event
CPR	Cardiopulmonary Resuscitation
CVA	Cerebrovascular Accident
DSMC	Data Safety Monitoring Committee
ECMO	Extra-Corporeal Membrane Oxygenation
ECPR	Extracorporeal Cardiopulmonary Resuscitation
EQ-5D-5L	EuroQol Quality of Life questionnaire
FIM	Functional Independence Measure
IHD	Ischaemic Heart Disease
OHCA	Out-of-hospital Cardiac Arrest
MRS	Modified Rankin Scale
PVD	Peripheral Vascular Disease
RIFLE	Risk, Injury, Failure, Loss of kidney function, and End-stage kidney disease.
ROSC	Return of spontaneous circulation
SAE	Serious Adverse Event
SAP	Statistical Analysis Plan
VA-ECMO	Veno-arterial-ECMO

2 Introduction

This Statistical analysis plan (SAP) has been written based on information from the study protocol version 2.0, dated 29 October 2018.

2.1 Preface

Survival from out of hospital cardiac arrest (OHCA) remains low despite advances in resuscitation science. Within London the London Ambulance Service (LAS) attended 10,116 OHCA in 2015/2016 and attempted resuscitation in 4389. Overall mortality was 91% for those in whom resuscitation was attempted, and even among the subset most likely to survive (“Utstein comparator group” – bystander witnessed cardiac arrests with a shockable rhythm), 35.5% of patients failed to achieve return of spontaneous circulation (ROSC) and the overall mortality was 68.5%. The mortality for those patients with witnessed cardiac arrests but in a non-shockable rhythm was 97.5% (3,353/3,440).

Hospital based extra-corporeal cardiopulmonary resuscitation (ECPR) uses an established technology (VA-ECMO), which provides greater blood flow and oxygen delivery during cardiac arrest than external cardiac massage [1]. The use of ECPR for in hospital cardiac arrest is associated with a stepwise improvement in survival to hospital discharge [2]. In-hospital ECPR is currently considered as a rescue therapy for selected patients [3]. There is no national protocol for its use and it has not been performed in a pre-hospital setting in the UK, nor investigated in a randomised controlled trial.

2.2 Purpose of the analyses

The Sub30 will investigate the technical and logistical feasibility of instituting pre-hospital ECPR within 30 minutes of collapse for selected patients in a geographical sector of Greater London. If pre-hospital ECMO flow or ROSC is feasible within 30 minutes of chest compressions starting, then a larger randomised controlled study of clinical and cost effectiveness is merited. Optimisation of the delivery of ECPR is vital, prior to a controlled study, in order to maximise any potential benefits for patients. Data from Sub30 will inform the design of such studies enabling an estimation of the size of any potential outcome benefits and the likely affordability for a healthcare service.

3 Study Objectives and Design

3.1 Design

The study is a single centre feasibility study of a complex intervention. The study aims to recruit six intervention patients. The study will only be performed between 8.00 am and 5.00pm on study days when the ECMO team is available. It is anticipated that this will be 2-3 days per week. Patients will be matched to other patients managed by LAS on non-study days, based on their suitability for ECPR in order to compare mortality between study and non-study days.

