Statistical methodology and analysis	
Descriptive statistics will be presented summarising the process and outcomes of the six patients.
 
Outcomes will be compared to other patients who were managed by London Ambulance Service on non-study days. Statistical matching to patients cared for concurrently with the study period will utilise a priori defined factors that may be associated with likely suitability for ECPR. Statistical matching will be individual, propensity score based and GenMatch guided.

Proposed start date	01 June 2019
Proposed end date	31 December 2022
Study duration	3 years 7 months

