## 7.2 Setting and timescale

The study will be undertaken in North East London over approximately 12 months. The study site is Barts Health NHS Trust.

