## 7.4 Patient identification / ECPR Team activation

On study days, the ECPR team will be active in a fast response blue light emergency response car provided by London's Air Ambulance. They will have no other clinical or non-clinical duties. On study days, the team will assemble at the Royal London Hospital and perform challenge/response checks on their equipment and vehicle. Once complete they will inform control that they are active and available. At various points in the day the team will be based in geographical areas where London Ambulance Service have attended the most cardiac arrests historically. At the end of the shift the team will inform control that they are standing down.

The team will be activated by the Advanced Paramedic Practitioner (APP) desk in the Emergency Operations Centre at London Ambulance Service. This desk screens in real time all calls to the emergency services that may be a cardiac arrest and dispatch additional APPs to the scene. They listen in on all calls where it is indicated on the pre-triage questions, asked by the call handler, that the patient is not breathing or has abnormal breathing. In addition, they screen calls as requested by the dispatchers. Their clinical experience at listening to calls will enable the LAS sit to identify trial subjects and dispatch the ECPR team as an additional emergency response within 2-3 minutes of the emergency call being placed. They will task the ECPR team if the estimated time of travel to the scene is 20 minutes or less.

All 'patients' for whom the team is activated will be included in the screening log. In addition to patients who are enrolled and receive ECMO, the log will indicate those people who were never assessed (as the team was stood down prior to arrival), those whose were assessed but clearly

did not meet inclusion/exclusion criteria (Section 8.2) and those in whom guidewires were inserted but were not formally enrolled in the study at the 20 minute time out (Section 8.5)

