8.1.5 Matching of controls to patients

Potential controls will be screened for inclusion and exclusion criteria including a cardiac aetiology. Only patients cared for concurrently with the study will be used. Controls will be individually matched to up to 5 patients, using age (within 5 years) and time of LAS attendance on scene (within 5 minutes). Matching with replacement will be performed but also matching without replacement in a planned sensitivity analysis.

8.2 Assumptions for analysis.

The analysis is descriptive and makes no assumptions about the data.

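### Controls are not limited to the study's hours or area, and the 5-minute matching factor is never defined as clock time or as a response interval

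*SAP*

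**What the plan says.** **Treated patients.** SAP 3.1 sets the hours: "The study will only be performed between 8.00 am and 5.00pm on study days". Protocol 7.2 sets the place: "The study will be undertaken in North East London over approximately 12 months". Protocol 7.4 sets the dispatch limit: "They will task the ECPR team if the estimated time of travel to the scene is 20 minutes or less". The clock hours appear only in the SAP.

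**Source of controls.** SAP 3.1: "Patients will be matched to other patients managed by LAS on non-study days, based on their suitability for ECPR". SAP 8.1.5 adds: "Only patients cared for concurrently with the study will be used". The protocol synopsis shows that this means the calendar period, not the hour: "Statistical matching to patients cared for concurrently with the study period". Candidates are then screened on the eligibility criteria. Protocol 6.1 and 6.2 contain no item on hour, area or travel time.

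**Matching.** SAP 8.1.5 uses individual matching on age within 5 years and "time of LAS attendance on scene (within 5 minutes", with a ratio of up to five. Its sentence reverses controls and patients; it is read here as up to five controls per treated patient. Protocol 10.2 lists age, LAS attendance time (both as closest matches) and presumed cardiac aetiology, and adds propensity-score and GenMatch matching. Neither document says whether attendance time is a time of day or an interval from the call. SAP section 6 reports the same variable, also undefined.

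**The concern.** The comparison is meant to set study days against non-study days. The treated group is also restricted by hour and place, and the control group is not, so the comparison may mix the intervention with differences by hour or area. Area has a visible route to outcome. Patients on ECMO go to one Heart Attack Centre (protocol 8.7), while refractory VF/VT under usual care goes to the nearest emergency department or heart attack centre (protocol 4.3).

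The undefined time factor means that two analysts following the same SAP could build quite different control groups, one uncontrolled for hour and the other very small.

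This is the plan's only controlled outcome estimate. Protocol 4.5 and SAP 2.2 say that the data will help to gauge possible outcome benefit for a later trial.

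**Working it through.** The plan gives no expected number of controls, so there is no figure to reproduce. Its source percentage checks: 199/560 = 35.5%.

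**Inputs from the documents**
- Study hours 08:00-17:00: 9 of 24 hours, 540 of 1,440 minutes (SAP 3.1).
- Callipers of 5 years and 5 minutes either side; up to five controls per case (SAP 8.1.5).
- Age range 18-65 (protocol 6.1).
- Six patients in up to 52 study days (protocol 7.3).
- About 12 months (protocol 7.2), or 3 years 7 months = 43 months = 1,310 days (synopsis).
- 199 Utstein-group patients a year without return of circulation (protocol 4.1).

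**Assumptions, not in the documents**
- Arrests are spread evenly over the day.
- The chance that a control is within 5 years of a case is 10/48 = 0.208 to 10/47 = 0.213 if ages are even, and 0.35 if they cluster.
- The 199 a year stand in for eligible controls. They cover all ages and only shockable rhythms, so this is an illustration and not a bound.

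**Reading 1: interval from call to arrival**
- Share of the pool outside study hours: (24 - 9)/24 = 15/24 = 62.5%.
- If response intervals are lognormal with median 6-8 minutes and SD 2.7-8 minutes (assumption), 49-83% of random pairs lie within 5 minutes. The factor selects little and does nothing about hour.

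**Reading 2: clock time**
- Time calliper: 10/1,440 = 0.694% of the day. Controls are confined to roughly 07:55-17:05, so hour is controlled.
- Joint match with age: 0.694% x 0.208 = 0.145%; x 0.213 = 0.148%; x 0.35 = 0.243%.
- Illustrative pool: 199 x 43/12 = 713. Expected matches per case: 713 x 0.145% = 1.0, up to 713 x 0.243% = 1.7.
- Cross-check within study hours: 713 x 9/24 = 267, and 267 x 10/540 x 0.208 = 1.0. The 540-minute denominator must go with the 267, not with the 713.
- With 52 study days removed: 199 x 1,258/365 = 686, giving 0.99-1.67 matches. Over 12 months: 199 x 313/365 = 171, giving 0.25-0.41.
- Poisson counts at 0.99-1.67: a given case has no match with probability 37% to 19%; all six have at least one with probability 6% to 28%.
- Pool needed for a mean of five: 5/0.00243 = about 2,060, to 5/0.00145 = about 3,450. Over 43 months that is about 575-965 eligible controls a year.

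**Area.** Neither reading involves location, so area is uncontrolled under both.

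**Pool after the fix.** Rate 6/52 = 0.115 per study day. Over 12 months: 0.115 x (365 - 52) = 36 eligible controls in study hours and area. With an interval match of 0.5-0.85 (assumption), 36 x 0.208 x 0.5 = 3.8 to 36 x 0.35 x 0.85 = 10.7, or about 4-11 per case. Over 43 months: 0.115 x 1,258 = 145, giving about 15-43.

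**The case against.** **The two problems do not occur together.** A reader might infer that the plan, as written, both compares daytime patients with all-hours controls and runs out of controls. It cannot do both. The 62.5% belongs only to the interval reading, and the scarcity only to the clock-time reading. This stands; the defect is that the plan does not choose.

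**Scarcity is not certain.** A reader might infer that clock-time matching finds almost no controls. That depends on the pool. Eligibility does not require a shockable rhythm, so the true pool could exceed 199 a year; the age limits push the other way. Protocol 10.2's closest-match wording, propensity scores and GenMatch need not drop a case for want of a 5-minute match. This stands too, so the scarcity figures apply only to the SAP's calliper. Those other methods still list neither hour nor area.

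**No bias is demonstrated.** A reader might infer that a survival difference would be wrongly credited to ECPR by a known amount. The documents give no survival by hour or sector, so neither size nor direction can be derived.

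**Materiality.** The analysis is descriptive with no hypothesis tests (SAP 3.7). One of six patients moves treated survival by 1/6 = 16.7 points, so chance will probably dominate. That lowers the stakes but does not justify an undefined variable.

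**Area is hard to define.** Dispatch depends on estimated travel from a position that changes during the day (protocol 7.4) or from an ambulance station (COVID-19 row of the protocol section 9 risk table). No fixed filter reproduces that exactly, and the documents do not show that the LAS extract carries location. The fix must allow for this.

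**Conclusion.** The point holds in a limited form. On the text alone, treated patients are restricted by hour, area and travel time; controls are restricted by none of these; and the only time-based matching factor has two incompatible meanings.

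- Interval reading: hour is uncontrolled, with 62.5% of the pool outside study hours if arrests are evenly spread.
- Clock-time reading: hour is controlled, but the SAP calliper takes 0.7% of the day and, with age, roughly 0.15% of a 24-hour pool (up to about 0.24% if ages cluster). That is about one match per case from an illustrative 713, against up to five wanted.
- Both readings: area is uncontrolled.

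The match counts rest on assumed pool sizes and age distributions; the missing restrictions and the missing definition do not. The documents do not support a claim of known bias, or any doubt about the primary feasibility endpoint, which uses no controls. What is affected is a descriptive survival comparison with six treated patients.

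**What to change.** In SAP 8.1.5 and protocol 10.2:

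1. Define the 5-minute factor as the interval from the emergency call to the first LAS arrival, and use the same definition in SAP section 6.
2. Restrict the main control pool to non-study-day arrests with call time within the team's operating hours (08:00-17:00). Where the LAS extract carries location, restrict it also to a study area defined in advance. Use all London in the same hours as a sensitivity analysis.
3. State what happens to a treated patient with no match.
4. Request the call-time and area fields beforehand, because LAS supplies the data in a single transfer after recruitment ends (protocol 10.2 and 13.3).

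The cost is a change of wording, two fields in the extract and a smaller pool: about 36 eligible controls over 12 months at the plan's own rate, or roughly 4-11 matches per case under the assumed age and interval distributions. The target of up to five would remain broadly reachable. A fixed area only approximates the 20-minute travel rule, and the report should say so.
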